2.3.2 Potential Benefits

GTx-024 9 mg once daily has been studied in 22 postmenopausal women with metastatic ER+ BC who have previously responded to hormonal therapy. The primary endpoint was assessed in 17 AR positive subjects. Six of these 17 subjects demonstrated CB (SD) at six months. In one subject with SD (RECIST 1.1), tumor regression of 27% in a single target lesion was demonstrated. Seven subjects in total (one subject with indeterminate AR status) achieved CB at six months. Among the seven subjects who achieved CB at six months, time to progression (TTP) was estimated as 10.2 months. The results also demonstrated that, after a median duration on study of 81 days, 41 percent of all subjects (9/22) achieved CB as best response and also had increased PSA, which appears to be an indicator of AR activity. As of the

Compound No.: GTx-024 Author: [name]

finalization of this protocol, the study is still ongoing with one subject whose disease remains stable beyond 336 days.

Preclinical data with GTx-024 suggests that it is also anabolic in bone and decreases bone turn over markers. Treatment with GTx-024 may decrease bone turn over as compared with other hormonal therapies for the treatment of hormone receptor positive BC. Stronger bone microenvironment may decrease metastases to bone or delay time to skeletal related events.

Compound No.: GTx-024 Author: [name]

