7 STUDY SCHEDULE

Subjects with CB at 24 weeks (Visit 6) will continue on therapy as long as they are still benefitting from the treatment. Treatment may continue for up to 24 months from the date of randomization (as long as they continue to demonstrate CB from the treatment during these 24 months).

Subjects who continue to demonstrate a CB from the study treatment at 24 months will be offered to continue in a safety extension study under a separate protocol.

All visits may be scheduled within a time window of \pm 7 days.

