7.3 Treatment Phase

The first dose of study drug will be administered on the day of randomization (Visit 2). GTx-024 will be administered daily for up to 24 months from randomization or until disease progression (whichever is sooner), subject's withdrawal of consent, or intolerability.

During the study treatment phase, the subjects will be scheduled for a visit every 6 weeks. Visit 7 at week 28 will only take place in subjects who have CR or PR at Visit 6 (week 24; see below).

The following tests and procedures will be performed during Visits 3, 4, 5, and 6 (weeks 6, 12, 18, and 24) in the treatment phase:

Review concomitant medications

Compound No.: GTx-024 Author: [name]

- Physical examination, including weight and vital signs (heart rate, respiratory rate, body temperature, blood pressure in a sitting position)
- ECOG performance status
- Blood sampling for: hematology, biochemistry, serum lipid profile, coagulation status, serum hormones, and PSA
- Urine analysis, if clinically indicated
- AE collection
- Subjects will be asked to complete a QoL questionnaire (EQ-5D-5L)
- GTx-024 drug accountability/dispensation

Radiologic assessments for anti-tumor effect will be done every 12 weeks whilst subjects receive treatment (Visits 4, 6, and thereafter). The same imaging technique must be used throughout the study in a given subject. Bone scans will be performed at screening and then every 12 weeks whilst subjects receive treatment (Visits 4, 6, and thereafter) in only those subjects with baseline bone metastases, or if clinically indicated. In addition, if any subject has CR or PR at Visit 6 (week 24), in compliance with RECIST 1.1 guidelines, a confirmation of the CR or PR (CT/MRI/bone scan) should be done 4 weeks later (Visit 7; week 28). The central imaging facility will also perform tumor volumetric assessment for the subjects undergoing CT scanning during Visits 4 and 6 (weeks 12 and 24). Blood sampling for CTC enumeration will be done at the same visits as the radiological assessments during the treatment phase; i.e., every 12 weeks whilst subjects receive treatment (Visits 4 and 6), but not at the confirmation of the CR or PR visit (Visit 7; week 28) or at Visits 8–13.

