11.4.2 Definition of analysis endpoints; primary, secondary, tertiary, exploratory, safety

Primary efficacy endpoint

Tumor response in terms of clinical benefit will be assessed by RECIST 1.1 criteria from centrally read CT scans obtained at the 24 week assessment. Tumor response is judged relative to baseline tumor assessments. An evaluable subject will be considered to have a response of CB if the assessment indicates CR, PR, or SD. The primary assessment is among evaluable subjects in the FAS at 24 weeks in each of the 9 mg and 18 mg arms. An evaluable subject who does not have a week 24 assessment for any reason remains in the evaluable subset of the FAS and is considered a failure to achieve CB (CR, PR, or SD).

Secondary efficacy endpoints

CBR in the FAS and PPS at 24 weeks in each of the 9 mg and 18 mg arms

The following secondary efficacy endpoints will be assessed among subjects in each of the 9 mg and 18 mg arms among the evaluable subjects, the FAS, and the PPS:

ORR (CR or PR assessed by RECIST 1.1 criteria) at 24 weeks

Compound No.: GTx-024 Author: [name]

- Best (confirmed) overall response rate (BOR). BOR is defined as the best observed response for each subject up to and including the EOT. Reponses of CR or PR should be confirmed by a repeat assessment at least 4 weeks later.
- PFS: PFS is defined as the time from randomization until objective tumor progression or death due to any cause. Subjects who have no PFS events will be censored at the date of the last adequate tumor assessment. If the subject has no post-baseline tumor assessments, they will be censored at the time of randomization
- TTP: TTP is defined as the time from randomization until objective tumor
 progression or death due to disease progression. Subjects who have not
 progressed will be censored at the date of the last adequate tumor assessment. If
 the subject has no post-baseline tumor assessments but is known to be alive, they
 will be censored at the time of randomization
- Duration of response: Duration of response, in responders, is defined as the period from the date of initial CR or PR until the date of disease progression or death from any cause. Only subjects with BOR of CR or PR (i.e., responders) will be included in the analysis of duration of response. Subjects with no documented progression or death after CR or PR will be censored at the last date at which they are known to have had the CR or PR

Tertiary efficacy endpoints

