11.4.3.3 Second efficacy analysis

 The exact 95% confidence intervals about the CBR at week 24 among subjects in the FAS and PPS in each of the 9 mg and 18 mg arms will be constructed

The following secondary efficacy analyses will be performed in subjects in each of the 9 mg and 18 mg arms among the evaluable subjects, the FAS, and the PPS:

- The exact 95% confidence interval about the ORR (CR or PR) will be constructed at week 24
- The exact 95% confidence interval about the BOR will be constructed at week 24
- PFS: Median PFS and 95% confidence intervals will be estimated by the Kaplan-Meier method and the survival function and associated 95% confidence intervals will be constructed at key time points
- TTP: Median TTP and 95% confidence intervals will be estimated by the Kaplan-Meier method and the survival function and associated 95% confidence intervals will be constructed at key time points
- Duration of response: Median duration of response and 95% confidence intervals will be estimated by the Kaplan-Meier method and the survival function and

Compound No.: GTx-024 Author: [name]

associated 95% confidence intervals will be constructed at key time points for responders

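### Duration of response, read literally, discards event-free time after CR/PR is lost, and the BOR interval is tied to week 24 although BOR runs to end of treatment

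*Combined protocol and SAP*

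**What the plan says.** **Duration of response.** Section 11.4.2 measures DoR "from the date of initial CR or PR until the date of disease progression or death from any cause", in subjects whose BOR is CR or PR. Responders with neither event "will be censored at the last date at which they are known to have had the CR or PR". Section 11.4.3.3 reports it by Kaplan-Meier: "Median duration of response and 95% confidence intervals", plus the survival function at key time points.

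**PFS and TTP in the same section.** For PFS: "Subjects who have no PFS events will be censored at the date of the last adequate tumor assessment". TTP uses the same date: subjects who have not "progressed will be censored at the date of the last adequate tumor assessment". TTP differs from DoR and PFS in counting only deaths due to progression.

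**Follow-up after response is lost.** SD is part of clinical benefit (CB). Section 7 states: "Subjects with CB at 24 weeks (Visit 6) will continue on therapy as long as they are still benefitting from the treatment". Section 7.3 adds: "Radiologic assessments for anti-tumor effect will be done every 12 weeks whilst subjects receive treatment".

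**Best overall response.** Sections 3.2.2 and 11.4.2 both run BOR to the end of treatment and require CR or PR to be confirmed; Section 11.4.2 asks for a repeat assessment at least 4 weeks later. Section 11.4.3.3 nevertheless constructs the exact 95% interval for BOR at week 24.

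**The concern.** The DoR definition and its censoring rule do not fit together. Censoring at the last CR/PR date would be coherent if losing the response ended DoR. Here it does not: only progression or death does. A responder who moves from PR to SD is still event-free and can still be under scheduled imaging. If she later progresses or dies, all her time since first response counts. If she does not, her time after the last CR/PR is thrown away. Event-free time is removed while events are kept, so DoR can look shorter than the PFS censoring date would make it look in the same subjects. The same variable enters the exploratory Cox models in Section 11.4.3.4.

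For BOR, two programmers could report different rates from the same data, depending on whether they follow the definition or the analysis bullet.

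**Working it through.** The documents give no numerical figure for DoR or BOR to reproduce. Their design figure, at least 3/18 then at least 9/44, has exact one-sided alpha 0.0236 and power 0.904. It therefore meets the stated 0.025 and 90%, and nothing below depends on it.

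**1. Direction.** The Kaplan-Meier estimate is S(t) = product over event times up to t of (1 − d/n), with d events among n at risk. Both censoring rules have the same DoR events, so d is the same. The last CR/PR date is on or before the last adequate assessment, so n under the literal rule is equal or smaller. Each factor is then equal or smaller, and so is S(t). The curves differ only if a responder without an event has a later adequate scan that is neither CR/PR nor progression, and an event falls in the removed interval. In 20,000 random small data sets with events fixed, the literal rule gave a higher curve in 0, a lower one somewhere in 13,884 and an identical one in 6,116.

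**2. One subject on the plan's calendar.** PR at week 24, confirmed at week 28, SD at weeks 36 to 72, no event:
- literal rule: 28 − 24 = 4 weeks, censored;
- PFS date: 72 − 24 = 48 weeks, censored;
- same subject with progression at week 84: 84 − 24 = 60 weeks, all counted.

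**3. A small group (assumed data).** Six responders, events at 24 and 36 weeks, four event-free at 48 weeks:
- PFS date: S(48) = 5/6 × 4/5 = 0.667. Greenwood SE = 0.667 × √(1/30 + 1/20) = 0.192.
- Literal rule, with one of the four last in PR at 12 weeks: S(48) = 4/5 × 3/4 = 0.600. SE = 0.600 × √(1/20 + 1/12) = 0.219.

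The shift is 6.7 points, against an SE of about 20.

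**4. Illustrative group size.** The documents give no rate of losing response without an event, so a range was assumed. The simulation used the plan's scan weeks, confirmed responders only, exponential time to progression with median 30, 48 or 72 weeks from response, and full or staggered follow-up to about week 96. The table shows how far the 48-week estimate falls below that with the PFS date, in percentage points.

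| Assumed share losing PR before progression | Loss independent of progression | Progression hazard doubled after loss |
|---|---|---|
| 0% | 0 | 0 |
| 10% | 0.5–1.5 | 0.3–0.9 |
| 25% | 1.4–4.5 | 0.8–2.7 |
| 50% | 4.3–12.7 | 2.1–7.2 |

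**5. How many responders.** In the earlier 9 mg study, "Six of these 17 subjects demonstrated CB (SD) at six months" (Section 2.3.2), so 0/17 had CR or PR at that time. The exact 95% upper limit is 1 − 0.025^(1/17) = 0.195, and 0.195 × 44 = 8.6, giving 0 to about 8 responders per arm. This is a rough guide only: it is response at six months, not best response, and it says nothing about 18 mg.

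**6. BOR, side by side.** A subject first in PR at week 36 and confirmed at week 48 is a responder by the definition and enters the DoR analysis, but a week-24 interval omits her. If confirmation must also fall by week 24, responses first seen at week 24 are lost too, because Section 7.3 puts their confirming scan at week 28. Section 11.3 plans no interim analysis, so week 24 is not a planned data cut.

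**The case against.** **Another reading of the DoR sentence.** Because DoR lasts until progression or death, the CR or PR in the censoring sentence can mean the response episode, which is still open while the subject is progression-free. The censoring date is then the last progression-free assessment and the gap vanishes. This is possible. The literal reading, the last date on which the response was CR or PR, is the more natural one, and the new wording settles it either way.

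**The separate SAP.** Section 11 defers further detail to a SAP. It does not withdraw either rule, and a SAP that followed them would carry them forward.

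**TTP.** A reader might infer that the DoR curve is also never higher than under the full TTP rule. That fails. Take progression at 8 and a non-progression death at 10 whose last scan was at 6. DoR counts both events, so S(8) = 1/2. TTP censors the death at 6, so S(8) = 0. The comparison holds only for the PFS date with the DoR events fixed.

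**The asymmetry is not unique.** Under the PFS rule, too, time after the last scan counts if the subject dies and is lost if she does not. The change narrows the asymmetry; it does not abolish it.

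**Continued scanning is not assured.** Section 8.1 bases treatment decisions on Investigator assessment, while efficacy uses central reads. A subject with central SD may stop for local progression, and scheduled imaging with it. The long run of SD in step 2 is a chosen example.

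**BOR numerator.** BOR covers all response categories, so the rate might seem undefined. Section 11.4.2 answers this: it equates responders with a BOR of CR or PR and asks for confirmation.

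**Conclusion.** Both points stand as drafting errors to correct, with modest consequences. On its literal wording, DoR uses a censoring date that does not match its own event definition, and the resulting curve is equal to or below the one with the PFS date. The BOR bullet contradicts the BOR definition.

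The direction rests on fixed DoR events and on the last CR/PR date being no later than the last adequate assessment. The size is unknown: the group figures above depend on assumed loss rates and are illustrations, and the effect may be zero. With few responders it would probably be small against sampling error.

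A reader might go further and infer that DoR is biased downward overall, or that its median is shortened by a known amount. The documents support neither. The comparison is with one other censoring date, informative dropout could act the other way, and the median depends on where the curve crosses 50% between scans. Nor is the trial's conclusion at risk: both endpoints are secondary and descriptive, the arms are not compared, and the 3/18 and 9/44 rules do not use them.

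**What to change.** In Section 11.4.2, replace the DoR censoring sentence with: *Responders with neither documented progression nor death are censored on the date of their last adequate tumor assessment, as for PFS; death from any cause remains an event.* Refer to PFS only, not TTP, so that deaths without progression are not programmed as censored.

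In Section 11.4.3.3, delete the week-24 reference from the BOR bullet and give the exact 95% interval for the proportion with confirmed CR or PR as best response up to end of treatment, which is how Section 11.4.2 defines responders.

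The cost is two sentences, carried into the SAP. No new data, visits or subjects are needed.

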11.4.3 Statistical methodology

11.4.3.1 Demographic data

Continuous demographic data (i.e., age, weight, height, and body mass index [BMI]) will be summarized by descriptive statistics (arithmetic mean, standard deviations, median, minimum, maximum, and total number of subjects). Categorical demographic

Compound No.: GTx-024 Author: [name]

data (i.e., gender, race, ethnicity, and ECOG performance status) will also be listed and tabulated in frequency counts and percentage.

11.4.3.2 Primary efficacy analysis

The primary efficacy analysis is based on rules as set forth in Simon's two stage (optimal) design as previously described, and is based on the proportion of evaluable subjects in the FAS who achieve CB at 24 weeks. At least 3/18 evaluable subjects must achieve CB in order for the arm to proceed to the second stage. If an arm proceeds to the second stage, ≥ 9/44 subjects must have CB at 24 weeks to deem the efficacy criteria to have been met in that arm. This is the minimum number of successes needed to rule out an unacceptably low, 10%, CB rate (lower limit of the 95% confidence interval). The exact 95% confidence intervals about the CBR at week 24 will be constructed.

11.4.3.3 Second efficacy analysis

 The exact 95% confidence intervals about the CBR at week 24 among subjects in the FAS and PPS in each of the 9 mg and 18 mg arms will be constructed

The following secondary efficacy analyses will be performed in subjects in each of the 9 mg and 18 mg arms among the evaluable subjects, the FAS, and the PPS:

- The exact 95% confidence interval about the ORR (CR or PR) will be constructed at week 24
- The exact 95% confidence interval about the BOR will be constructed at week 24
- PFS: Median PFS and 95% confidence intervals will be estimated by the Kaplan-Meier method and the survival function and associated 95% confidence intervals will be constructed at key time points
- TTP: Median TTP and 95% confidence intervals will be estimated by the Kaplan-Meier method and the survival function and associated 95% confidence intervals will be constructed at key time points
- Duration of response: Median duration of response and 95% confidence intervals will be estimated by the Kaplan-Meier method and the survival function and

Compound No.: GTx-024 Author: [name]

associated 95% confidence intervals will be constructed at key time points for responders

11.4.3.4 Tertiary efficacy analysis

The following tertiary efficacy analyses will be performed in subjects in each of the 9 mg and 18 mg arms among the evaluable subjects and among the FAS:

- PSA changes from baseline to each scheduled assessment will be described and tested for a significant change from baseline. Percentage change from baseline will be summarized and analyzed as well
- QoL: The EQ visual analog scale (VAS) will be summarized by descriptive statistics at baseline and each assessment. Mean changes from baseline will also be summarized using descriptive statistics and 95% confidence intervals. EQ-5D-5L single item scale scores (mobility, self-care, usual activities, pain/discomfort, and anxiety/depression) will be summarized by means of frequency counts at baseline and at each assessment
- CTCs: Changes in the number of CTCs from baseline to each scheduled assessment will be described and tested for a significant change from baseline
- Duration of prior CB: The impact of duration of prior CB on the current CB
 response will be explored in an exploratory way using logistic regression models
 with and without other covariates. The impact of duration of prior CB on PFS, TTP,
 and duration of response outcomes will be assessed in a Cox proportional hazards
 model with and without other covariates
- Time from diagnosis of metastases to randomization: The impact of time from diagnosis of metastases to randomization on the current CB outcome will be explored in an exploratory way using logistic regression models with and without other covariates. The impact of time from diagnosis of metastases to randomization on PFS, TTP, and duration of response outcomes will be assessed in a Cox proportional hazards model with and without other covariates
- Tumor volumetrics: The effect of GTx-024 9 mg and 18 mg on tumor volume will be described visually using waterfall plots

Compound No.: GTx-024 Author: [name]

 GTx-024 and GTx-024 glucuronide plasma concentrations will be assessed for their association with CBR at week 24 using logistic regression by creating binary variables for the concentrations by dichotomizing at the median concentration at week 24

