3 OBJECTIVES

3.1 Study Objectives

The **primary efficacy objective** of this trial is to estimate the CBR at 24 weeks (defined as complete response [CR], partial response [PR], or SD) (by RECIST 1.1) of GTx-024 9 mg and of GTx-024 18 mg given PO daily in subjects with estrogen receptor positive and androgen receptor positive (ER+/AR+) BC who have centrally confirmed AR+ status.

Secondary efficacy objectives:

 Estimate the CBR at 24 weeks (by RECIST 1.1) of GTx-024 9 mg and 18 mg in all subjects randomized who receive at least one dose of study medication (the full analysis set [FAS]) regardless of AR status as determined by the central laboratory

The following secondary efficacy objectives apply to both centrally confirmed AR+ subjects (the evaluable subset of the FAS) as well as to all subjects in the FAS:

- Estimate the objective response rate (ORR; defined as CR or PR) (by RECIST 1.1) of GTx-024 9 mg and 18 mg at 24 weeks
- Estimate the best overall response rate (BOR) of GTx-024 9 mg and 18 mg
- Estimate the progression free survival (PFS) of subjects receiving GTx-024 9 mg and 18 mg
- Estimate the TTP of subjects receiving GTx-024 9 mg and 18 mg
- Estimate duration of response (time from documentation of tumor response to disease progression or death) of subjects receiving GTx-024 9 mg and 18 mg

Tertiary objectives:

The following tertiary efficacy objectives apply to both centrally confirmed AR+ subjects (the evaluable subset of the FAS) as well as to all subjects in the FAS:

Assess the effect of GTx-024 9 mg and 18 mg on serum PSA

Compound No.: GTx-024 Author: [name]

- Assess the effect of GTx-024 9 mg and 18 mg on Quality of Life (QoL) as measured by EQ-5D-5L³
- Assess the effect of GTx-024 9 mg and 18 mg on circulating tumor cells (CTCs)
- Assess the impact of duration of prior CB on outcome
- Assess the impact of time from diagnosis of metastases to randomization on outcome
- Describe the effect of GTx-024 9 mg and 18 mg on tumor volumetrics
- Assess the effect of plasma concentrations of GTx-024 and GTx-024 glucuronide on CBR at 24 weeks

Safety objective:

To describe the safety profile of GTx-024 9 mg and 18 mg PO daily in subjects with ER+/AR+ BC with centrally confirmed AR+ as well as in all subjects randomized and treated.

Pharmacokinetic objective:

To describe the plasma concentrations of GTx-024 and GTx-024 glucuronide at each of the assessed time points.

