4 STUDY DESIGN

This is an open label, multicenter, multinational, randomized, parallel design Phase 2 study to assess the efficacy and safety of GTx-024 in postmenopausal subjects with ER+/AR+ BC. Subjects will be randomized to receive either GTx-024 9 mg or 18 mg given PO daily for up to 24 months. Each dose arm will be treated independently and each assessed for efficacy using Simon's two-stage (optimal) design¹. Subjects will be randomized in a 1:1 fashion to one of the two dose arms. Randomization will be stratified by subjects presenting with bone only metastases and all other subjects, and further by setting of immediately preceding therapy (adjuvant setting or metastatic setting) in order to balance the proportion of subjects with these presenting features in each dose arm. There is no intent to statistically compare the two dose arms, but to determine whether either or both doses result in an acceptable CBR, defined as the proportion of evaluable subjects (i.e., subjects with centrally confirmed AR+ and who receive at least one dose of study drug) with either CR, PR, or SD by RECIST 1.1 at week 24, consistent with 30% while maintaining an acceptable safety profile. Given such a result, future exploration of GTx-024 in ER+/AR+ BC would be warranted at that dose level.

Thirty-six to 88 (36–88) subjects with centrally confirmed AR+ who receive at least one dose of study drug (evaluable subjects) will be needed for primary efficacy analysis purposes and will be a subset of the FAS. Thirty-six to one hundred and eighteen (36–118) subjects, including replacement subjects, will be randomized in a 1:1 fashion to receive a daily PO dose of either GTx-024 9 mg or 18 mg. Thirty of the aforementioned subjects may be considered replacement subjects to account for lack of centrally confirmed AR+ status or for the rare subject who is randomized but does not receive study drug (assumes 25% of enrolled subjects are not evaluable for the primary efficacy analysis). Other statistical parameters that are part of the sample size calculation are α = 0.025 (one-sided) and power = 90%. The first stage in each study arm will be assessed among the first 18 evaluable subjects. If at least 3/18 subjects achieve CB (defined as CR, PR, or SD) at week 24, the arm will proceed to the second stage of recruitment up to a total of 44 evaluable subjects per arm. Otherwise, the arm will be discontinued for lack of efficacy. Statistical significance, i.e., rejection of

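### The exposure-response analysis splits concentration at the median, apparently within each dose arm, and so has low power for moderate concentration effects on CBR

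*Combined protocol and SAP*

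**What the plan says.** Section 3.1 lists a tertiary objective: "Assess the effect of plasma concentrations of GTx-024 and GTx-024 glucuronide on CBR at 24 weeks". Section 11.4.3.4 gives the method. The association will be assessed "using logistic regression by creating binary variables for the concentrations by dichotomizing at the median concentration" at week 24. The lead-in to all the tertiary bullets says that the analyses "will be performed in subjects in each of the 9 mg and 18 mg arms among the evaluable subjects and among the FAS".

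The bullet does not say whose median is meant. Read with the lead-in, the natural meaning is one median and one model per arm. Section 11.4.3 contains no model with continuous concentration and no model across both arms; Section 11.4.3.6 adds only descriptive statistics. The cut point is particular to this bullet: for duration of prior clinical benefit and time from diagnosis of metastases, the same section plans logistic and Cox models without prescribing a split.

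**The concern.** The objective concerns concentration, but the planned covariate is a high/low flag. Everyone on the same side of the median is treated alike, however far from it.

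On the by-arm reading there are two further losses. First, high and low mean different concentrations in the two arms, so the two odds ratios per analyte do not combine into one exposure-response statement. Second, the doubling of dose, which is the exposure difference the trial creates by randomisation, never enters the model.

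At stake is a tertiary result, but it is the only planned analysis linking exposure to CBR. Section 2.2 argues for 18 mg partly on exposure grounds and expects the data to inform the design of later trials that would settle the dose. An uninformative null could be misread as absence of an exposure effect.

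**Working it through.** **1. The plan's own figures.** Section 11.4.3.2 sets these rules: "At least 3/18 evaluable subjects must achieve CB in order for the arm to proceed to the second stage", and then "≥ 9/44 subjects must have CB at 24 weeks to deem the efficacy criteria to have been met in that arm". An exact search for the Simon optimal design (10% v 30%, one-sided alpha 0.025, power 90%) returns the same design, with exact alpha 0.0236 and power 0.904. The enrolment ceiling also reproduces: 88 / 0.75 = 117.3, rounded up to 118. These figures concern the primary endpoint. No power or sample size is stated for the exposure-response analysis.

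**2. Inputs.**
- From the protocol: 44 evaluable per arm, 1:1 allocation, 9 mg v 18 mg, CBR 30% as the design alternative.
- Assumed, because the protocol gives no value: log-normal concentrations with between-subject log-SD 0.4 (CV = √(e^0.16 − 1) = 42%); exposure proportional to dose; a log-linear effect with odds ratio 2.0 per doubling; mean CBR 30% over both arms; two-sided 5% tests; a concentration available for all 44. The last is favourable, since Section 11.4.3.7 does not impute missing values.

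**3. Hand approximation.** The slope is β = ln 2 / ln 2 = 1 per log unit. Power ≈ Φ(z − 1.96), where z is the effect times the square root of the information and p(1 − p) = 0.21.
- Median split, one arm: the halves differ by 2 × 0.4 × √(2/π) = 0.638 log units, and the information is 44 × 0.21 / 4 = 2.31. So z = 0.638 × 1.520 = 0.97, power about 16%.
- Pooled median split: the arm means lie 0.347 either side of the centre, so the halves differ by about 0.864. Information 88 × 0.21 / 4 = 4.62, z = 1.86, power about 46%.
- Pooled continuous with arm term: only within-arm variance 0.16 counts. Information 88 × 0.21 × 0.16 = 2.957, z = 1.72, power about 41%.
- Pooled continuous without arm term: variance 0.16 + 0.347² = 0.280. Information 5.18, z = 2.28, power about 62%.

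**4. Simulation, same inputs, likelihood-ratio tests.**

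| Analysis | Hand | Simulated |
|---|---|---|
| Median split, each arm | 16% | 14-17% |
| Median split, at least one arm | – | 29% |
| Pooled median split | 46% | 42% |
| Pooled log concentration, arm term | 41% | 37% |
| Pooled log concentration, no arm term | 62% | 59% |

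Repeat runs differ by up to about three points. The either-arm figure agrees with 1 − 0.86 × 0.83 = 29%. With no effect, two 5% tests give 1 − 0.95² = 9.75% nominally; simulation gives about 11%, against about 5% for a single pooled model.

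**5. What low means in the two arms.** Under these inputs, the share of low 18 mg subjects lying above the 9 mg median is 1 − 2Φ(−ln 2 / 0.4) = 1 − 2Φ(−1.73) = 92% (83% at log-SD 0.5).

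**6. Other assumed values, 44 per arm.**
- Odds ratio 2.8, log-SD 0.4: 22-30% per arm, 45-47% in either arm, 65-69% pooled with arm term, 88-92% without.
- Odds ratio 1.5 to 2 with CV 30-70%: 7-34% per arm, 14-51% in either arm.
- Odds ratio 1.5 with CV 50%: 11% per arm, and only 32% for the pooled model without an arm term.
- CBR 10% at 9 mg and 30% at 18 mg, produced wholly by concentration: either-arm detection 43%, 77% and 96% at CV 30%, 50% and 70%.
- Response flat above the 9 mg median exposure, odds ratio 2.0-2.8 below it, log-SD 0.4: pooled continuous 7-10%, either-arm median split 13-17%. The latter is little above its own 11% false-positive rate.

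**The case against.** **The arm-specific median is inferred.** A generic lead-in covering seven bullets supplies it. This stands. Under a pooled median the dose contrast is used and there is one test per analyte. The flag would then coincide with dose arm for about 81% of subjects (Φ(0.347 / 0.4) = Φ(0.87)), so it would be largely a dose label, and its power would still be below that of the unadjusted continuous model (42% v 59%). The wording needs settling on either reading.

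**Single-arm power should not be set against a pooled test.** This also stands. The fairer base is 29% in either arm. Against it the arm-adjusted model gains about 8 points and the unadjusted model about 30, so most of the gain comes from the dose contrast.

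**The protocol points to a plateau.** Section 2.2 reads the SHBG data as showing AR activity to be maximal from about 10 mg, while also proposing a second mechanism at 15-20 mg. If response is flat over the trial's range, the pooled model has no advantage. This is a real limit on the claim.

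**The design treats the arms separately and disclaims comparison.** A regression on measured concentration is not a test between arms, though without an arm term it draws mainly on the between-dose difference.

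**The analysis is tertiary and a separate SAP is to follow.** True. Sections 11 and 11.4.3.8 leave further analyses to that SAP, so a continuous model is not excluded. But Section 11.4.3.4 already fixes the method and names no alternative.

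A reader might go further and infer that a real concentration effect will usually be missed, or that a null result would say nothing. The documents support neither. They give no between-subject variability and no exposure-effect size; steep effects with wide variation would mostly be detected (77-96% in step 6), and an odds ratio with its interval still bounds steep effects.

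**Conclusion.** The point holds in a limited form. The planned median split has low power for moderate concentration effects, clearly below that of a continuous log-concentration model across both arms as long as response keeps rising with exposure. At an odds ratio of 2.0 per doubling the comparison is 29% in either arm against 37% (arm term) or 59% (no arm term). These figures rest on assumed log-SD, dose proportionality, log-linearity and complete concentration data; none comes from the protocol. They also rest on the by-arm reading, which is the natural one but is not stated. Even the better model is weak for small effects. The primary analysis and its decision rules are untouched.

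**What to change.** In Section 11.4.3.4, and in the SAP when written:

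- Fit one logistic model per analyte across both arms, with log concentration as a continuous covariate.
- Name in advance one model, with or without the arm term, as the main analysis and the other as sensitivity. Treating both as equal tests would raise the chance of at least one false positive to about 8%.
- Report the odds ratio per doubling with its 95% CI.
- Check for non-linearity or a plateau with a quadratic term.
- If a median split is kept, make it a descriptive table with a stated cut point common to both arms.

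The cost is wording only: no extra samples, visits or subjects. The downside is the assumed log-linear shape, which matters here because of the plateau suggested in Section 2.2; the quadratic term is a partial check.
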